8.2.5.2 Secondary Outcomes

There will be several secondary outcome measures to assess the clinical safety, feasibility, usability, and acceptability of the system (see Table 6).

Clinical safety

To examine safety, two outcomes will be captured. Firstly, patients at both sites will have a retrospective case review of both general and ophthalmic electronic health records at 90 days after their initial operation. Complications will be identified from patient's medical records related to any unplanned eye-related clinical episode.

Secondly, all cataract surgery patients at Imperial were historically followed up face-to-face between 3-4 weeks post-surgery in a dedicated post-op clinic. Any complications requiring a change in patient management at slit lamp review or from attending eye casualty services (as the Oxford site does not normally perform face-to-face follow-ups) will be compared with the decisions made by **DORA** and the clinician. If Imperial changes their method of follow-up due to the COVID-19, assessment for complications will be done by checking hospital medical records as is done at the Oxford site.

Feasibility

Feasibility will be assessed by examining the proportion of autonomous calls that were completed without needing any intervention from the supervising clinician. All interruptions or clarifying questions of the supervised call will be logged; the supervising clinician will be asked to log the reason for asking clarifying questions. If clarifying questions were asked because the clinician felt that there was insufficient information for either individual symptoms or to make a management plan, the clinician's management plan before and after clarifying questions will be captured to see if clarifying questions changed the management plan.

Usability

Usability will be assessed using questions presented to patients following calls delivered by online and paper surveys distributed to participants. These questions will be drawn from the System

Usability Scale (SUS) and Telehealth Usability Questionnaire (TUQ; see 13.4 Appendix 4 for a sample survey) [14,15].

Acceptability, satisfaction, and appropriateness

DORA's acceptability, satisfactoriness, and appropriateness will be assessed during qualitative interviews with a subset of the patients. These semi-structured interviews will provide an opportunity for patients to provide more in-depth feedback about what they liked about **DORA** and any barriers to use that they experienced during the call (see 13.5 Appendix 5 for a sample topic guide). The supervising clinician will also be asked to provide feedback about their level of satisfaction with the system and any safety concerns they might have.

Patients' willingness to recommend **DORA** to others will also be assessed at the end of the call [20]. **DORA** will calculate a net promoter score (NPS) by asking patients "on a scale of 1 to 10, how likely would you be to recommend this automated service to a friend or colleague." **DORA** will follow up by asking patients to "tell me why you gave that score."

Cost-effectiveness

Cost-effectiveness will be examined by collecting and analysing health economic data before and during the study. The costs of implementing **DORA** will be compared with historical data about the costs of the usual standard of care.

| Secondary Outcome | Outcome Measure | | | |
|-----------------------|---|--|--|--|
| Clinical Safety | Complications identified from patients' electronic health records up to 90 days following cataract surgery | | | |
| | Congruence between complications identified and management planned in DORA call and face-to-face follow up (Imperial) Comparison to data from patients attending eye casualty (Oxford) | | | |
| Feasibility | Proportion of autonomous calls that were completed without needing any intervention from the supervising clinician | | | |
| | Clinician-reported reasons for asking clarifying questions | | | |
| Usability | System Usability Scale (SUS) [14,17] | | | |
| | Telehealth Usability Questionnaire (TUQ) [15] | | | |
| | Qualitative feedback from semi-structured interviews | | | |
| Acceptability | Qualitative feedback from semi-structured interviews | | | |
| Satisfaction | Qualitative feedback from semi-structured interviews, Net Promoter Score (NPS) | | | |
| Appropriateness | Qualitative feedback from semi-structured interviews | | | |
| Cost-effectiveness | Comparison of the costs of implementing DORA and the costs of the usual standard of care | | | |
| Identify improvements | Synthesis of all of the outcome measures previously described | | | |

Table 6. Secondary Outcome Measurement

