5 STUDY SUMMARY

Table 3. Study Summary

| Table 3. Study Summary | |
|--------------------------|--|
| Study Title | A clinical investigation of an autonomous phone conversational agent for cataract surgery follow-up |
| Short title | Autonomous telephone follow-up after cataract surgery |
| Study Design | The study will be a multi-centre, mixed-methods clinical investigation to develop evidence regarding the feasibility, acceptability and potential effectiveness of DORA . |
| Study Participants | The study will include adults (aged 18 years or older) who are on the waiting list for either their first or second eye cataract surgery at Oxford or Imperial. To be eligible, the patients must have no history of significant ocular comorbidities and have a routine surgery with no intraoperative complications. |
| Planned Size of Sample | The planned sample size is 591 patients, split mostly equally between Oxford and Imperial clinical sites (see Table 1 for details on how this estimate was produced). |
| Follow up duration | Imperial: patients will receive the standard face-to-face appointment within a few days of having the autonomous call (dependent on current Covid-19 restrictions). |
| | Oxford: there will be no face-to-face follow-up for patients at the Oxford site as this is the standard of care. |
| | At both sites, an additional 3-month follow-up period where unplanned eye-related clinical visits will be recorded and assessed. |
| Planned Study Period | The total duration of the study will take up to 3 years, including the recruitment of patients, intervention refinement period, main intervention period, and analysis of results. |
| Research Question/Aim(s) | The aim of the study is to assess the evidence for the safety of using DORA to deliver autonomous cataract surgery follow-up assessments. This ability will be evaluated in comparison to an expert human clinician to assess the research question: Can DORA identify which patients need clinical follow up after a cataract operation? |

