8.2.3 Intervention(s)

DORA uses a variety of AI technologies to deliver the patient follow-up call, including: speech transcription, natural language understanding, a machine-learning conversation model to enable contextual conversations, and speech generation. Together, these technologies cover the input, processing and analysis, and output needed to maintain a natural conversation. **DORA** is configured to deliver calls through a telephone connection as a real-time, stand-alone system: the operator inputs individual patient details to initiate the call and completes a summary in the electronic health record (EHR) afterwards. The call that patients will receive from **DORA** will include several conversational elements:

- Greeting and introduction
- Identification of patient
- Cataract follow-up questions
- Patient's queries
- (Decision)
- Questions about acceptability
- Closure of call

The entire conversation will be supervised by a clinician. This clinician will be able to interrupt the call at any point if the system fails, the patient struggles to interact with it, or **DORA** does not collect sufficient information from the patient. The call will proceed in the following stages (visualised in Figure 5):

- 1. Stage 1. Call initiation: the supervising clinician will confirm the suitability of the patient, input their details, and initiate the call.
- 2. Stage 2. Symptom assessment: Once the call has begun, **DORA** will verify the identity of the patient and proceed through the cataract follow-up questions. As the patient answers the questions, both **DORA** and the supervising clinician will record their independent assessment about the clinical significance of the symptoms elicited.
- 3. Stage 3. Management plan decision: Once all of the follow-up questions have been asked, **DORA** and the supervising clinician will independently make and record their decisions about the management plan for the patient. **DORA** will then inform the patient of the clinician's decision about their management plan (i.e. whether specialist review is required or not).
 - Stage 3a: Optionally, if required, the supervising clinician can ask additional clarifying questions.

Figure 5. Flow Diagram of DORA's call with patient

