8.5 Data Analysis

8.5.1 Statistical Methods for Primary Outcome

The primary analysis will be the calculation of a kappa statistic of inter-observer (**DORA** & clinician) reliability of the decision made. Additionally, the outcome of the assessment will be compared with the 'real' complication rate determined by hospital medical records. This will be established by identification of any hospital presentation within 90-days after the last call. Given the specialist nature of ophthalmology services it can be assumed that patients will present through the eye casualty or clinic services offered by each site. Patients who present to the hospital eye service will be analysed on a case-by-case basis to ensure that complications that were missed by **DORA's** original assessment and complications that developed later can be differentiated. This analysis will provide baseline sensitivity and specificity data for use in preparing subsequent evaluations of efficacy.

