13.6 Appendix 6. Imperial Historical Recruitment Audit Data

Purpose

To provide real world evidence for assumptions made in modelling of recruitment numbers and study planning.

Audit

We audited all bookings in the cataract one-stop-clinic for the month of October 2020. After discussion with the head of the cataract pathway, it was felt this was the most representative of what the cataract pathway will likely look like in May-July 2021 assuming there is COVID recovery of a similar trajectory to the first wave. It is anticipated there will be 3 consultant-led one-stop clinics running in July to address the backlog. Of note, the general pre-assessment pathways have not been audited.

Key findings

Clinic capacity and utilisation - All October one-stop data

- 33 patients were booked across 4 clinics
- 8.25 patients on average per clinic
- 88% (29/33) attended their one-stop appointments

Conversion rate

- Of all patients booked, 76% proceeded for surgery (25/33)
- Or, of those attending, 86% proceeded to surgery (25/29)

Demographics

- Mean age was 71.5
- This was the first eye for 52% of patients

Inclusion/Exclusion

- 100% (29/29) of those attending were listed for routine cataract surgery
- 10% (3/29) required a translator (Tamil, Punjabi, Arabic)
- 1 patient (3%) had dementia and would not have been able to consent
- Overall, of all attending patients, 76% (29/33) would have been eligible for trial inclusion.

Withdrawal

- No patients in this cohort had unexpected surgical complications
- 1 patient (4%) attended AnE before follow up with a corneal abrasion and would have been withdrawn from **DORA** per our current protocol.

Follow up

- 95% (24/25) of patients attended post-op follow up
- **21%** (7/25) of patients had a documented complication requiring management change at their post-op followup.
 - \circ 6 of these patients were uveitis
 - 4 of which were given maxidex and discharged
 - 1 was given maxidex with phone follow up

- 1 was given maxidex and listed for 2nd eye.
- 1 patient has post-op cystoid macular oedema and maxidex requiring medical retina review.

Pathway

- The mean time between one-stop appointment and surgery was **9.88 days.**
 - The range was from 2 days to 62 days
 - **16 patients** had their operations in under 1 week
- Mean time between surgery and first follow up was 24.33 days.
- A number of patients were followed up under the 21 day point

Comparison with initial estimates

| | Imperial | Imperial |

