A Clinical Investigation of an Autonomous Phone Conversational Agent for Cataract Surgery Follow-up

NCT05213390

30 August 2022

Statistical analysis plan

Using the variables:

- doraoutcomeupdate (0 = pass, no review, 1 = fail, needs review)
- supervisoroutcomeupdate (0 = pass, no review, 1 = fail, needs review)

Primary outcome: Agreement between Dora and clinician for overall outcome decision and each symptom (x5)

- Inter-rater reliability (kappa)
- Accuracy (%)
- Data regarding true/false negatives/positives

	Clinician: follow-up (1)	Clinician: no follow-up (0)
Dora: follow-up (1)	ТР	FP
Dora: no follow-up (0)	FN	TN

• Sensitivity, specificity, AUC

Secondary outcomes

Clinical safety: Comparison with real complication rate

*Note: please do this analysis three times, once for each of the three complication measures
Data regarding true/false negatives/positives (Tables 2-3)

	Complications: 3 month audit	No complications: 3 month audit
Dora: follow-up	ТР	FP
Dora: no follow-up	FN	TN

- Sensitivity, specificity, AUC
- Variables
 - Dora follow up: "doraoutcomeupdate"
 - Complications:
 - "hospital-review-within-3-months"
 - 0 = no hospital review, 1 = hospital review
 - "unexpected-change-management"
 - 0 = no unexpected change management, 1 = unexpected change management

EUR ING [name] MA MSc MBA MPA PhD CEng FBCS Associate Professor of eHealth

"unplanned-hospital-rev"

• 0 = no hospital review, 1 = hospital review

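### The SAP's unplanned-review measure is not a valid reference standard for DORA's sensitivity, specificity and AUC: Imperial's scheduled visit hides complications from it, and at Oxford its result depends on undefined coding

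*Protocol*

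**What the plan says.** Protocol section 8.2.5.2 (Clinical safety) describes a record review at both sites, 90 days after the operation: "Complications will be identified from patient's medical records related to any unplanned eye-related clinical episode". The Study Summary (section 5) agrees, promising "an additional 3-month follow-up period where unplanned eye-related clinical visits will be recorded and assessed".

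The SAP's clinical safety section gives a two-by-two table of DORA's decision by complications or no complications at the 3-month audit, with sensitivity, specificity and AUC. It instructs: "please do this analysis three times, once for each of the three complication measures". One of the three is "unplanned-hospital-rev", coded 0/1 with no definition of unplanned. The others are "hospital-review-within-3-months" and a variable for an unexpected change in management. None is named as the main reference.

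Four other places bear on this:

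- Section 6 (Stage 5) and section 8.2.4: Imperial patients have a scheduled face-to-face visit whether or not they take part, and the call is made within the 3 days before it. The Study Summary says Oxford has no face-to-face follow-up.
- Section 8.2.3: DORA "will then inform the patient of the clinician's decision about their management plan". The clinician's decision, not DORA's, therefore determines whether a review is arranged.
- Section 8.5.1, on the comparison with the real complication rate: "This will be established by identification of any hospital presentation within 90-days after the last call". That is a wider event and a different window from section 8.2.5.2.
- Appendix 6 (Imperial audit): 7/25 "of patients had a documented complication requiring management change at their post-op followup".

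**The concern.** A reference standard for sensitivity has to be able to register a true complication however it came to light. This one registers it only if the patient came back outside the planned pathway. At Imperial the planned pathway includes a visit intended to find complications, timed just after the call. A complication present at the call is likely to be found there, and the SAP table then files that patient under no complications.

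Objective 2 (section 7.5) is to establish baseline sensitivity and specificity for postoperative complications, and section 8.5.1 intends such figures for use in later evaluations. A table with these labels would be read as detection accuracy when it largely measures how visits were classified.

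**Working it through.** **Inputs from the documents**

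- Site numbers (Table 7). The common multiplier is 0.70 × 26 × 0.85 = 15.47. Imperial: eligibility 0.80 × 0.80 × 0.80 × 0.95 = 0.486, × 10 × 2 × 15.47 = 150.5; and 0.90 × 0.80 × 0.80 × 0.95 = 0.547, × 8 × 2 × 15.47 = 135.4. The sum is 285.9, printed as 286. Oxford: 0.90 × 0.80 × 0.90 × 0.95 = 0.616 gives 228.6 + 76.2 = 304.8, printed as 305.
- Complications at the scheduled Imperial visit (Appendix 6). The audit prints 21% beside 7/25, but 7/25 = 28%; 7/33 = 21.2% uses all booked patients as denominator. Both are carried below.

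**Assumed, because the documents give no value:** true sensitivity 0.90, true specificity 0.90, and a complication rate of 10% where the audit's rate is not used.

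**Step 1. Imperial patients affected, if all complications surface at the scheduled visit**

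- 0.28 × 286 = 80.1
- 7/33 × 286 = 60.7

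**Step 2. Imperial table under the two readings (28% rate, no new complications after the visit)**

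| Reference event | TP | FN | FP | TN |
|---|---|---|---|---|
| Complication confirmed at any visit | 72.1 | 8.0 | 20.6 | 185.3 |
| Unplanned review only | 0 | 0 | 92.7 | 193.3 |

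The 72.1 correct flags join the false positives (20.6 + 72.1 = 92.7), and the 8.0 misses join the true negatives (185.3 + 8.0 = 193.3). Specificity falls from 0.90 to 193.3/286 = 0.68. With these inputs it is 0.90 − 0.80 × rate: 0.73 at 7/33 and 0.82 at 10%.

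Sensitivity has no events to be computed from. If 1% of the patients without a complication later develop one and present unplanned, it becomes 0.10. That is merely the assumed flag rate among patients who were well at the call, so it carries no information on detection.

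**Step 3. Oxford**

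Let *q* be the share of DORA's correctly flagged complications whose review is coded unplanned, and *s* the share of its misses that surface as an unplanned episode. Then

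measured sensitivity = 0.90*q* / (0.90*q* + 0.10*s*).

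Take *s* = 1, a clinician who agrees with DORA on these patients, and no new later complications. At 305 patients and a 10% rate there are 30.5 complications, of which DORA flags 27.4 and misses 3.0 (both cut to one decimal).

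| *q* | Measured sensitivity |
|---|---|
| 0 | 0.00 |
| 0.25 | 0.225/0.325 = 0.69 |
| 0.50 | 0.45/0.55 = 0.82 |
| 1 | 0.90/1.00 = 0.90 |

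The complication rate cancels, so these values are the same at 2%, 5% and 28%. DORA's performance is identical in every row; only the coding differs.

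**Step 4. Dependence on clinician agreement**

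At *q* = 0, with a 10% rate and 1% later events, measured sensitivity at Oxford is 0.05 if the clinician confirms all of DORA's correct flags, 0.35 if 90% and 0.51 if 80%. Patients whose flag is not confirmed are not sent for review and can still present unplanned.

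**Step 5. AUC**

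For a yes/no decision, AUC is the mean of sensitivity and specificity, so it inherits both distortions.

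**The case against.** A reader might infer something stronger: that the measure can never register a complication the call caught, so that DORA's sensitivity is driven towards zero. The documents do not support that.

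- Unplanned is undefined, and nothing says how a review ordered because of the call is coded. The nearest usage, the withdrawal rule in section 8.3.1.3, counts some planned appointments as unplanned review. Oxford has no routine visit, so a call-triggered review there could reasonably be coded unplanned. Step 3 shows that coding even a quarter of them so gives 0.69.
- A patient whom the clinician flagged could still attend unplanned before the arranged review, or later with a new problem. True positives therefore do not require DORA and the clinician to disagree.
- The distortion is not all against DORA, because Imperial's scheduled visit also hides its misses.
- The safety analysis does not rest on this table. The other two SAP measures can register planned or call-triggered reviews. Section 8.2.5.2 also compares complications found at slit lamp review with the call decisions, and section 8.5.1 uses any hospital presentation with case-by-case review.

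These points limit the size and reach of the problem, but they do not make the table valid. The SAP still orders it and ranks none of the three measures. The any-review measure may have the opposite fault if routine Imperial visits count. The case-by-case review separates missed from later complications and is silent on those the call caught.

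**Conclusion.** The point stands for one of three secondary safety tables. At Imperial it follows from the plain meaning of unplanned together with the visit schedule, and needs no assumption about call-triggered reviews. About 80 of 286 patients would be misfiled at 28% (about 61 at 7/33) if all complications surface at the scheduled visit. The remaining sensitivity reflects only later or self-presenting events. The audit covers only 25 operated patients, so the count is indicative.

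At Oxford the documents do not fix the result. The range of 0.00 to 0.90 rests on an assumed true sensitivity of 0.90, all misses self-presenting, and a clinician who agrees with DORA.

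One condition applies: section 8.2.5.2 allows Imperial to drop the face-to-face visit because of COVID-19 and rely on hospital records. Imperial's result would then depend on the same undefined coding as Oxford's.

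**What to change.** In the SAP:

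1. Do not compute sensitivity, specificity or AUC against "unplanned-hospital-rev". Report it as a missed-event rate: unplanned reviews among patients DORA passed and, separately, among those the clinician passed.
2. Name one reference event for sensitivity and specificity: a complication requiring a change in management, confirmed at any visit in the window, whether scheduled, call-triggered or unplanned. Record the visit type and report by site. With the assumed inputs and complete capture of complications, this returns the true 0.90 and 0.90.
3. Define unplanned and state how scheduled and call-triggered reviews are coded.
4. Reconcile section 8.2.5.2 (unplanned episodes, 90 days from the operation) with sections 8.2.4 and 8.5.1 (90 days from the call; any hospital presentation in 8.5.1). Correct the audit's 21% or its denominator.

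The cost is SAP wording and one visit-type field in a record review that is already planned, with no extra patients or visits. The downside is that one planned accuracy table becomes a rate.

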8.4.3 Methods of Data Collection

8.4.3.1 Quantitative data collection

The key data to be collected are **DORA** and the clinician's decisions. This will include data on symptoms as well as an overall assessment. Both **DORA** and the clinician will separately record their decisions about symptoms, clinical assessment, and management plan. **DORA** will record the decisions in the **DORA** database, which will be accessed by the study team during the evaluation to compare against the clinician decisions. Usability of the system will be assessed using the SUS and

TUQ questionnaires (see 13.4 Appendix 4). These will be delivered to all participants shortly after they have had the call with **DORA** via an online or paper survey (see Figure 6).

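### The NPS is collected only by DORA, at the end of a supervised call, so it may miss patients whose calls ended early and may be too high

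*Protocol*

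**What the plan says.** Under Acceptability, satisfaction, and appropriateness (Protocol 8.2.5.2), willingness to recommend DORA "to others will also be assessed at the end of the call". DORA puts the question itself. It "will calculate a net promoter score (NPS) by asking patients" the following: "on a scale of 1 to 10, how likely would you be to recommend this automated service to a friend or colleague". It then asks for the reason.

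Section 8.2.3 lists the elements of the call. "Questions about acceptability" come after the decision and just before closure, which is presumably where the NPS item sits. The same section states: "The entire conversation will be supervised by a clinician". On problems during the call it says: "This clinician will be able to interrupt the call at any point if the system fails, the patient struggles to interact with it". It does not say what happens to the rest of the script after such an interruption. Clarification is a sub-step of Stage 3: "Optionally, if required, the supervising clinician can ask additional clarifying questions".

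Table 6 gives two measures for Satisfaction: interviews with a subset of patients, and the NPS. Of the SUS and TUQ questionnaires, section 8.4.3.1 says "These will be delivered to all participants shortly after they have had the call with" DORA, online or on paper. The sample survey in Appendix 4 contains demographics, SUS and TUQ, with no recommend question. The topic guide in Appendix 5 has none either. The SAP does not mention the NPS.

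**The concern.** Two features of the collection could push the score the same way.

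- **Selection.** Whether a score exists depends on whether the call got as far as its last item. The reasons a call might not get there, system failure or a struggling patient, are also reasons a patient might score low. Missingness may therefore be linked to the quantity being measured.
- **Who is asking.** The patient gives the rating aloud to the system being rated, on a supervised line. Section 8.6 recognises social desirability bias for the interviews but does not raise it for the NPS.

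What is at stake is the credibility of the one number assigned to Satisfaction. Section 5.2 says the study arrangements are meant to secure an independent assessment of the company's technology. A rating that only that technology gathers and computes is a weak fit with this aim. The primary agreement analysis is not affected.

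**Working it through.** The documents state no target NPS, expected NPS, completion rate or NPS sample size, so there is no figure to reproduce. The check has three parts.

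**1. Which patients can have a score?**

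| Type of call | Does it reach the NPS item? | Basis |
|---|---|---|
| Runs without intervention | Yes | Item is at the end of the call (8.2.5.2) |
| Clinician asks clarifying questions at Stage 3a | It may | Clarification belongs to the decision stage; the acceptability questions follow it (8.2.3) |
| Ends, or is taken over, before the last item | Not stated; no other route is given | 8.2.3, Appendices 4 and 5, SAP |

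Only the third row creates the selection risk. Its frequency is not given. Feasibility (Table 6) counts calls needing no intervention, which is not the same split, because its complement also includes clarified calls from the second row.

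**2. How far could the reported NPS be off through selection?**

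Let f be the share of calls without a score, C the NPS of patients who answer, and M the NPS the others would have given. NPS is taken as percent promoters minus percent detractors, so it runs from −100 to +100.

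- NPS for all patients = (1 − f) × C + f × M
- Reported minus all-patient NPS = f × (C − M)

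f, C and M are assumptions. With C = +50, the excess in points is as follows (call counts are f × 591, the recruitment expected in Table 7):

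| f | Calls | M = +75 | M = +50 | M = 0 | M = −50 | M = −100 |
|---|---|---|---|---|---|---|
| 5% | about 30 | −1.25 | 0 | 2.5 | 5 | 7.5 |
| 10% | about 59 | −2.5 | 0 | 5 | 10 | 15 |
| 20% | about 118 | −5 | 0 | 10 | 20 | 30 |

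Worked cell: f = 10%, M = −100 gives 0.10 × (50 + 100) = 15, so the all-patient NPS is 0.90 × 50 − 0.10 × 100 = +35.

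**3. How does that compare with sampling error?**

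For an NPS of +50 made up of 60% promoters and 10% detractors (assumed), the 95% half-width is 100 × 1.96 × √[(0.60 + 0.10 − 0.50²) / n]. With n = 591 this is 5.4 points; with n = 520, the required sample size in 8.3.2.1, it is 5.8. At f = 10%, the selection error is close to the half-width if M = 0 and more than twice it if M = −100.

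This arithmetic covers selection only. The documents give nothing from which to size the effect of DORA asking about itself.

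**The case against.** A reader might infer that every patient DORA failed goes unscored by design. The documents do not support that. An interruption is not described as ending the call, and clarified calls may go on to the NPS item. The flow diagram (Figure 5) could not be consulted here and may show the path after an interruption. What stands is that the text is silent on calls that do stop early.

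A reader might also infer that the NPS is biased upward as a matter of fact. That needs some calls without a score and lower scores among those patients, and neither is documented. The excess is zero if the two groups feel alike and negative if the missing patients are happier. Nothing in the documents shows that answering DORA, or having a clinician supervise, raises scores.

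Nor is Satisfaction without other evidence. TUQ item 37, on overall satisfaction, reaches all participants outside the call. Because 8.2.5.2 has interruptions logged, it could be compared between interrupted and uninterrupted calls. Interviews also feed the outcome, and Appendix 5 asks about using DORA again. This stands as a partial cross-check. It could suggest the direction of any selection but cannot supply a recommend score, and Table 6 assigns the TUQ to Usability. Interviewees are drawn from strata formed from the survey (8.4.1.1), so survey non-responders may be missed there too. Appendix 4 is labelled a sample, so the final survey could differ.

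Finally, survey non-response may be selective as well. That is a fair argument against making the survey answer the sole reported NPS, and the fix below respects it.

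**Conclusion.** The point holds as a risk arising from how the score is collected. The NPS comes solely from DORA, as the last item of a supervised call, with no second route and no rule for calls that stop before it. It may therefore be too high. The amount cannot be known from the documents. Under the assumption of +50 among patients who answer, 5% to 20% of calls without a score would inflate it by 2.5 to 10 points if the missing patients' NPS is 0, and by 7.5 to 30 points if all are detractors. The latter is the extreme case.

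Importance is low. The NPS is one of two measures for one of eight secondary outcomes in Table 6, and no threshold or decision is attached to it. It is worth acting on because the remedy is cheap.

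**What to change.** 1. Add the same recommend question, on the same scale and with the same request for a reason, to the Appendix 4 post-call survey.
2. Report the in-call NPS and the survey NPS side by side, each with its denominator. Declare neither free of selection.
3. Report how many calls did not reach the in-call item, by logged interruption status (none, clarification only, other interruption).
4. Give a sensitivity bound for the in-call NPS that counts patients without a score as detractors: (1 − f) × C − 100 × f, with the observed f and C.

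The SAP should carry items 2 to 4 in a line or two. The cost is one more survey question, with its follow-up, and a short tabulation; no new visit or system is needed. The downside is that survey response may be lower than in-call response, which is why both figures are kept. The bound addresses selection only. The survey answer, given away from the call, is what addresses patients rating DORA to DORA.
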